2. STRESS VARIABLES

2.1 Academic stress questionnaire at university (CEAU).

This questionnaire prepared by García - Ros & Pérez - González (2012), (ANNEX 05) assesses possible stressful

situations in the university environment and consists of a total of 21 items. The participants' responses indicate the level of perceived stress in each situation using a Likert-type response scale with 5 options ranging from “no stress” (1) to “a lot of stress” (5). The internal consistency of this instrument, in this study, has a .819 once Cronbach's α has been analyzed.

This questionnaire is divided into 4 subscales, which are:

- Academic obligations (OA): consists of 8 items (1, 5, 7, 9, 10, 11, 14 and 15) that assess the level of stress generated in students by carrying out academic work and exams, the lack of time to develop activities, academic overload, performing required work, excess responsibilities and study-related activities. Its internal consistency is .675 using Cronbach's α .
- Record and future prospects (EF): provided with 6 items (16, 17, 18, 19, 20, 21) that, like the previous one, measure the stress generated by the anticipation of problematic situations or future academic situations, such as completing the studies within the stipulated deadlines, obtaining high grades, maintaining or obtaining a scholarship, the choice of subjects and itineraries during the career and family pressure to obtain good results. Its internal consistency in this study is .691 using Cronbach's α .
- Interpersonal difficulties (ID): using 4 items (6, 8, 12, 13) determines the level of stress that can produce problems or conflicts with classmates and teachers, as well as that related to competitiveness with peers. Its internal consistency is .758 through the analysis of Cronbach's α .
- Expression and communication of own ideas (EC): through 3 items (2, 3, 4) stress is evaluated in the moments that students are required to present and express their own ideas in the classroom in the presence of all their colleagues. Its internal consistency is .725 according to Cronbach's α .

2.2 Academic Stress Coping Scale (A-CEA)

The coping scale, known as A-CEA (González Cabanach et al., 2010), is a subscale of the CEA questionnaire, an instrument made up of three scales, which is used to assess academic stressors (E-CEA), stress responses (R-CEA) and stress coping strategies (A-CEA). (ANNEX 06).

The A-CEA scale is made up of 23 items, formulated to evaluate the cognitive and behavioral strategies used by the student when facing situations of academic stress. It is a scale with Likert-type responses to each item, in which the student can choose between five options: Never (1), Sometime (2), Many times (3), Many times (4) and Always (5). The reliability of the A-CEA scale has a general Cronbach coefficient for this study of .885. In turn, this coping scale is divided into 3 factors that are specified below:

- Factor 1. Positive Reevaluation: This dimension groups nine items (1, 3, 4, 5, 6, 14, 17, 18 and 19) that present different ways of coping aimed at creating a new positive meaning about the problem or academic difficulty. This factor underlines its active and positive character in propositions such as “When I face a problematic situation the night before the exam I try to think that I am prepared to do it well” or “When I face a complicated situation, in general, I try not to give it importance to the problems”. Its internal consistency according to Cronbach's α is .668.
- Factor 2. Search for Social Support: It includes seven items (2, 8, 10, 13, 20, 21 and 23) to evaluate an active and behavioral type of coping, based on the student's search for information and advice, as social support to the problem, and also of understanding on the part of other people, as emotional support with what he experiences. Its internal consistency according to Cronbach's α is .727.
- Factor 3. Planning and management of personal resources: It includes seven items (7, 9, 11, 12, 15, 16 and 22) that refer to the activation of strategies based on analysis and reasoning to change the problem situation, and that denote a type of behavioral and active coping. Its internal consistency according to Cronbach's α is .741 for this study.

2.3 Sociodemographic variables questionnaire

A third questionnaire (ANNEX 03) to collect necessary information on sociodemographic variables such as age, gender, place of residence and type of home. This questionnaire also aims to collect some data referring to their academic life, such as the average grade for access to the university and the degree completed. The ad-

hoc questionnaire consists of a total of 11 items and all questions are made in a clear and concise manner so that the answer is free from ambiguity.

3. ACADEMIC PERFORMANCE

The final average grade of the first academic semester will be analyzed comparing by groups.

To dispense the questionnaires, a computer tool will be designed through the Google Forms platform, which will allow the creation and distribution of said questionnaires digitally, which will facilitate their dissemination and subsequent coding. The link to said questionnaire will be sent to the participants by email, which will be completed electronically without the need to contact the researcher. Once completed, the results will be automatically sent to the main researcher, subsequently being encoded in a statistical database.

In order to compare the individual results of the PRE and POST intervention questionnaires, they will be identified with the identification code of the participants, without thus making it possible to identify the subjects.

STATISTICAL ANALYSIS PLAN OF THE RESULTS

For the coding and analysis of the data, the statistical program IBM® SPSS Statistics version 22 will be used. For the treatment of categorical variables, tables of absolute and relative frequencies will be made, which will be analyzed using Pearson's Chi-square.

In the case of quantitative variables, the mean and standard deviation will be obtained as the measures of central tendency and dispersion index. The Kolmogorov-Smirnov test will be performed to check the normality of the distribution in the event that the sample obtained is the expected one (greater than 30 individuals). If the distribution is normal, parametric tests will be performed to assess differences between groups. Statistically significant differences will be sought between the quantitative variables of the groups by means of a student's t test for independent measures. and repeated measures ANOVA to compare the measures collected at different times in the same group. If the population does not follow a normal distribution of the variable under study, non-parametric tests will be performed to determine the differences between groups. Friedman's test for paired samples and Kruskal Wallis's test for independent samples. In all cases, a 95% confidence interval and a significance level less than or equal to 0.05 will be established.

FORECAST OF POSSIBLE SIDE EFFECTS THAT MAY OCCUR

Anticipation of possible risks / damages and mechanisms to reduce harm or distress to a minimum

No risk is foreseen during the performance of the technique. The study will meet the ethical requirements of the Helsinki Declaration of the World Medical Assembly (WMA) on ethical principles for medical research involving human beings.

Provision of measures to minimize pain, stress, physical or emotional risk.

Study participation does not have harmful risks to health. No study complications and no adverse effects of the applied techniques are anticipated. They will be warned in advance that during the first two sessions of the treatment they could perceive slight alterations of the sleep phases, exceptionally.

Forecast of remuneration or gratification for participation in the study

The study subjects have as a common link their own health or that of the future patient, therefore, all of them can benefit from knowing the applicability of the proposed technique in improving the quality of life. No economic remuneration is foreseen, however, the student will be rewarded with a special recognition in the subjects that he / she takes related to research methodology.

Sensitivity to the needs and perspectives of the people participating in the project

No long-term benefit or harm is anticipated, as the technique is safe and tested in healthy patients.

Provision of contracting liability insurance

The different Faculties have civil liability insurance that will cover possible liabilities.

SCHEDULE

The total duration of the project is estimated to be 8 months.

- A. Project design.
- B. Authorization of the Center and request for approval by the Ethics Committee for Clinical Research.
- C. Recruitment of Personnel and Users.
- D. Therapeutic intervention and data collection.
- E. Statistic analysis.
- F. Evaluation and interpretation of results.
- G. Drafting of results report and dissemination of results.

	M AND S AND S							
CHORES	1	2	3	4	5	6	7	8
TO								
B								
C								
D								
AND								
F								
G								

QA

1.- Identification of collectors:

Each collector will be assigned a code that will be included as the first digit in the patient's identification code in the 1-xxxx format. Each collector is responsible for the data dump so the collector digit matches the data dump.

Recorder	Code
Person I	1
Person II	2

Person III	3
Person IV	4

2.- Quality audits:

Since it is estimated that the total sample will be registered during the first month, a quality audit will be carried out on a weekly basis. In them, the following will be carried out:

- Ascending ordering of the data: revision of the variable date of inclusion and time of exposure.
- Exploration of the variable.
- List of Frequencies for the variables: age, sex, marital status, use of drugs and perception of health.

According to this procedure, we could detect inconsistencies in the data dump, as well as identify the person who executed it, guided by the code assigned to the registrar already mentioned in the first section. In addition, the code could be associated with the name of the document when it is edited and saved, so that it would be known who last entered or evaluated the document. In both situations, in the event of detecting an error, the person in charge would be notified immediately to correct it.

3.- Audit mechanism: Cross Audit

Each logger, weekly the first month, and biweekly the following months, will review the data dumped from another logger in the team from the last review to date, according to a random sequence established by the principal investigator. The scheme to follow would be the following:

4- Ethical and legal considerations. Procedures to keep information and comply with legal considerations regarding data protection.

All data will be collected by computer in an encrypted Excel document (Microsoft Office Excel 2019 MSO 64-bit program). They will be downloaded in electronic format from the Google Forms platform, and a database will be created whose access will be encrypted, which will make it only accessible through a key known

exclusively to the researchers responsible for each project center.

The pseudonymization used in completing the questionnaires will make the personal data collected in no case identifying a natural person.

The estimated time for the coding and analysis of the results is estimated at 2 months, after which time the database will be erased, keeping only the statistical data. The destruction will be done by means of computer erasure by means of a program that allows deleting specific folders, eliminating hard drives and filling in empty spaces on the disk, so that the elimination technique is safe and the deleted information is not allowed to be recovered again. Statistical data will be kept for the time necessary for the adequate dissemination of the results.

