"LET'S TALK ABOUT COLLEGE STUDENT SLEEP: AN
INNOVATIVE NON-INVASIVE NEUROMODULATION
TREATMENT TO IMPROVE SLEEP QUALITY AND
ACADEMIC PERFORMANCE: RANDOMIZED
CLINICAL TRIAL" (USLEEP)

ID: USLEEP

[NCT ID not yet assigned] 15/11/2021

TITLE OF THE PROJECT

"Let's talk about sleep in college student: an innovative treatment based on non-invasive neuromodulation to enhance the sleep quality and academic efficiency: Randomized controlled trial" (USLEEP)

CENTERS AND RESEARCHERS:

- Dra. [name] (IP. Physiotherapist. PhD. University of Las Palmas de Gran Canaria).
- [name] [name] (Physiotherapist. University of Las Palmas de Gran Canaria).
- [name] (Physiotherapist. PhD. Alfonso X el Sabio University)
- [name] (Physiotherapist. PhD. Pontifical University of Salamanca).
- Dra. [name] (Biologist. PAD, PhD. Pontifical University of Salamanca)
- Dra. [name] (Physiotherapist. PhD. Pontifical University of Salamanca)
- [name] (Physiotherapist. PT, PhD. University of Alcalá de Henares)

ABSTRACT

Currently, disorders such as insomnia, narcolepsy or circadian rhythm disturbances are the most common among college students. The concern about the quality of sleep of university students, future professionals of the world, must be crucial for the scientific community, as well as for university professors and professors. Innovative electrotherapy technologies such as non-invasive neuromodulation NESA are showing effects on improving sleep quality, concentration and stress, so the objective of this project is to carry out a triple-blind randomized clinical trial with first-year science students from three universities. The design was made up of an intervention group with NESA technology and another control group in each of the centers. Where the quality of sleep will be analyzed,

This multicenter project hopes to demonstrate that non-invasive NESA neuromodulation can be a preventive treatment for the maintenance of sleep quality during stressful periods such as university exams, as well as being able to modulate perceived stress and translate into an improvement in student performance.

STUDY JUSTIFICATION:

INTRODUCTION:

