Randomized clinical trial with passive control, triple blind (for the patient, the physiotherapist applying the technique and evaluator), with a parallel and multicenter design. The study will have two arms, the intervention group will undergo neuromodulation treatment with the NESA XSIGNAL® device and the control group will not carry out any intervention, but both will be evaluated for the same variables at the same times.

SCOPE AND STUDY POPULATION:

Multicenter study whose collaborating entities correspond to the University of Las Palmas de Gran Canaria, Alfonso X el Sabio University, the Pontifical University of Salamanca and the University of Alcalá de Henares. The study population will be students from the collaborating universities, corresponding to first-year health sciences degrees. For the selection of the sample, a non-probabilistic convenience sampling will be carried out, which allows selecting those accessible cases that agree to be included.

CALCULATION OF THE SAMPLE:

The present study is proposed as a pilot study due to the absence of similar studies in this field that allow a

calculation of the adjusted sample size. For this, 80 participants will be included, who must meet the established selection criteria.

CRITERIA FOR SELECTING THE PARTICIPANTS

INCLUSION CRITERIA.

- Healthy people
- Be enrolled in a degree in health sciences at the partner universities in the study in the first year.
- Optimal cognitive abilities and mentally competent to participate in the study.
- In cognitive conditions to complete the study questionnaires
- Have an optimal command of the Spanish language to complete the questionnaires.
- Signing of the informed consent for participation

EXCLUSION CRITERIA.

- Present some of the contraindications for a treatment with NESA X SIGNAL®: Pacemaker or other electrical surgical device, internal bleeding, do not apply electrodes on skin in poor condition, with ulcerations or wounds, acute febrile processes, pregnancy, acute thrombophlebitis and / or phobia of electricity, and pregnant.
- Combine another pharmacological treatment that influences the variables to be evaluated during the study.

ELIMINATION CRITERIA.

- Missing an intervention session of the 10 scheduled sessions.

RECRUITMENT OF PARTICIPANTS AND EVALUATION PROCESS.

Phase 1. Dissemination of the study

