The dissemination of the participation of the subjects in the study will consist of making an initial contact through the teachers responsible for each center. Once informed, the students will receive an email with the complete information sheet containing the description of the study, the objective, the justification, the risks and benefits derived from participation, everything related to the protection of their personal data and the way of contacting the researcher in charge of each center (ANNEX 01). In the same actions, the established selection criteria will be reported.

Phase 2. Call for anamnesis of those interested in participating in the study and selection of study subjects.

Phase 3. Acceptance of participation in the study by signing the informed consent (ANNEX 02)

Once the consent is signed, the participant will fill in the participant's demographic characteristics questionnaire (ANNEX 03) and measures of baseline variables.

Next, the participant will be summoned to the laboratory of the corresponding university for the application of the evaluation intervention within the corresponding deadlines and indicated in the information sheet of the study.

RANDOM ASSIGNMENT:

Patients who agree to participate will be randomly assigned to one of the 2 arms of the study (real device or control), using a fixed-size block design generated by the data manager to guarantee balanced randomization for each of the arms and in each of the participating universities. The assignment process will be carried out hidden and will be carried out by the support researcher in the Unit indicated for this study. Each research subject will be assigned an identification code corresponding to correlative numbers from 1 to 80, with 1-20 subjects from the UPSA, from 21-40 students from the Alfonso X el Sabio University, from 41 to 60 students from the University of Las Palmas and from 61 to 80 from the University of Alcalá.

BLINDING:

The intervention to which the subjects have been assigned, the specialist and the researcher who collects the information and performs the follow-ups will be blinded. Data analysis will also be performed in a blinded fashion.

INTERVENTION PROTOCOLS

For neuromodulation:

Group 1: Application of Nesa microcurrents through the NXSIGNAL® generator twice a week.

The volunteer subjects of the study are treated with the NXSIGNAL® device in sessions of 60 minutes, twice a week and for 5 weeks (10 sessions).

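### The semester grade is compared between arms without the access grade, which loses precision, and without university, which overstates the SE if universities differ and arms stay balanced within them

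*Combined protocol and SAP*

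**What the plan says.** Section 3, Academic performance, states: "The final average grade of the first academic semester will be analyzed comparing by groups". The statistical analysis plan then gives two between-group options for a quantitative variable: a "t test for independent measures" if the distribution is normal, and Kruskal-Wallis if it is not. Repeated-measures ANOVA and Friedman's test are also named, but they compare time points and do not fit a grade recorded once. The plan adds: "In all cases, a 95% confidence interval and a significance level less than or equal to 0.05 will be established". No covariate, centre term or stratified test appears anywhere.

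Two relevant variables are available:

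- **University.** Under Random assignment, fixed-size blocks are used "to guarantee balanced randomization for each of the arms and in each of the participating universities", with 20 participant codes for each of four universities. The Abstract instead refers to "first-year science students from three universities".
- **Access grade.** Section 2.3 describes a questionnaire that covers academic life, "such as the average grade for access to the university and the degree completed". Phase 3 of recruitment has it completed once consent is signed: the "demographic characteristics questionnaire (ANNEX 03) and measures of baseline variables".

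**The concern.** Student performance is part of the main goal, and academic performance is also a secondary objective. At most 40 students per arm contribute one grade each. The outcome has no pre-intervention value, and the access grade is the only measure of prior attainment that the documents describe.

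The two omissions act differently:

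- **University.** If arms are balanced within universities, differences between universities cancel from the arm difference but stay in the t test's pooled SD. The estimate is as precise as it would be with adjustment, but the reported SE is too large and the test is conservative.
- **Access grade.** Its omission makes the estimate itself more variable than it need be.

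The choice has to be made beforehand. The data-protection section has the database erased after about two months of coding and analysis, with only statistical data retained. If that means summaries, an adjusted analysis may not be possible later. In addition, Kruskal-Wallis itself gives no interval for the arm difference.

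**Working it through.** The plan has no figure to reproduce: 80 is a pilot number with no effect size, SD or power.

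**Inputs from the documents.** 80 students; two arms balanced within university; 20 codes in each of four universities, hence an inferred 10 per arm in each; significance level 0.05 (two-sided assumed).

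**Assumptions.** Grade in SD units; effect 0.5 SD; within-university correlation r of access grade with semester grade 0.2 to 0.6; share v of grade variance between universities 0 to 20%, with university effects drawn at random in each simulated trial; all 80 analysed.

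**Planned t test.** SE = √(2/40) = 0.224. The difference detectable with 80% power is (1.960 + 0.842) × 0.224 = 0.63 SD. Power for 0.5 SD is about 60%.

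**Omitting university.**

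- True SD of the arm difference: √[(1 − v)/20], which is 0.212 at v = 10% and 0.200 at v = 20%.
- Expected pooled variance used by the t test: (1 − v) + v × 30/39, which is 0.977 and 0.954. The SEs are √(0.977/20) = 0.221 and √(0.954/20) = 0.218, so 4% and 9% too large.
- Simulation (20,000 trials per cell): mean reported SE 0.220 and 0.217 against true SDs of about 0.213 and 0.201, so 3% and 8% too large. Type I error is 3.9–4.1% and 3.4% instead of 5%.
- If v is instead the share realised among these four universities, the pooled variance is (1 − v) + v × 40/39. The excess is then about 6% and 12%, with type I error of 3.8% and 2.7%.

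**Omitting the access grade.** Relative to the model with arm and university, the variance ratio is (1 − r²)(1 + 1/73). This is 0.973, 0.851 and 0.649 at r = 0.2, 0.4 and 0.6, so the true SD falls by 1.4%, 7.7% and 19.5%. Break-even is r² = 1/74 = 1.35%, or r = 0.12.

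**Power for 0.5 SD** (simulation, four universities, 10 per arm in each):

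| v | r | t test | + university | + university and access grade |
|---|---|---|---|---|
| 0 | 0 | 59.9% | 59.9% | 59.3% |
| 0 | 0.2 | 60.1% | 60.0% | 61.3% |
| 0 | 0.4 | 59.4% | 59.3% | 66.3% |
| 0 | 0.6 | 59.5% | 59.5% | 78.2% |
| 10% | 0.2 | 61.9% | 64.9% | 66.0% |
| 10% | 0.4 | 60.7% | 63.6% | 70.8% |
| 10% | 0.6 | 61.6% | 64.6% | 82.1% |
| 20% | 0.2 | 62.1% | 68.7% | 70.0% |
| 20% | 0.4 | 63.4% | 69.8% | 76.4% |
| 20% | 0.6 | 63.4% | 69.9% | 86.7% |

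University adds about 0, 3 and 6–7 points at v = 0, 10 and 20%. The access grade adds about 1, 7 and 17–19 points at r = 0.2, 0.4 and 0.6. For r = 0.2 to 0.6, the full model's type I error is 4.7–5.1%.

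**Sensitivity checks**, at (r = 0.2, v = 0), (0.4, 10%) and (0.6, 20%):

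- *Three universities:* t test 59.6/61.6/63.3%, full model 60.8/71.6/86.2%.
- *Uneven loss* (assumed 0, 2, 4 and 6 active-arm students lost by university, 68 analysed): t test 51.6/52.7/53.6%, full model 51.3/61.3/78.1%. The t test's type I error is 5.1/4.9/4.2%.
- *Left-skewed residuals, skewness −0.7:* Kruskal-Wallis 61.3/62.1/61.4%, full model 61.2/71.3/86.6%.
- *Left-skewed residuals, skewness −1.4:* Kruskal-Wallis 73.4/68.3/63.9%, full model 62.1/71.7/86.4%.
- *Access grade 10% missing at random:* university-mean fill 60.5/70.7/84.7%, complete cases 56.1/66.8/82.2%. Type I error with the fill is 4.8–5.0%.

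**The case against.** - **Pilot status.** The trial is proposed as a pilot without a power calculation, and the planned test is valid, if slightly conservative. Gains quoted at an assumed 0.5 SD may therefore overstate the importance. This limits the weight of the point. But the plan still tests at 0.05, and precision matters in a pilot too.
- **The plan may not use the t test.** When normality fails it moves to Kruskal-Wallis, so the t test is not always the comparator. With strong left skew and r = 0.2, the model loses about 11 points when universities do not differ (73.4% to 62.1%) and about 5 at a 10% share (70% to 65%). At r = 0.4 with no university differences the two tie at 68%. This stands: across all the scenarios examined the change runs from about −11 to +23 points.
- **Balance within university is not secured.** Block size is not stated, and the Elimination criteria include "Missing an intervention session of the 10 scheduled sessions". Only the active arm has sessions, so losses could be uneven. In the uneven-loss scenario at a 10% share, the reported SE is only about 1% too large (0.2425 against 0.2401). This also stands; the SE claim needs the balance condition.
- **Smaller points.** The interval sentence may mean only a 95% confidence level. The retained statistical data are not defined. ANNEX 03 is not visible, so the scale and completeness of the access grade are unverified. None of these changes the omission or the remedy.

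**Conclusion.** The concern holds. The planned comparison is unbiased but uses neither the variable on which allocation is balanced nor the only described baseline measure of attainment. Against the t test, and under the stated assumptions (normal grades, no loss, 10 per arm in each of four universities, 0.5 SD effect), the full model gains about 1 to 23 power points. It loses 0.6 point if both variables are uninformative. The gain may be small, because r and v are assumed and not taken from the documents. The overstated SE also requires that universities differ and that arms stay balanced within them. The exception is strong skew with a weak covariate, where the rank test does better. The change should be made because it is cheap, but the validity of the trial does not depend on it.

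**What to change.** For this outcome, replace the t test/Kruskal-Wallis choice with a pre-specified linear model of semester grade on arm, university and access grade. Report the adjusted arm difference with its 95% confidence interval whatever the Kolmogorov-Smirnov result, and keep Kruskal-Wallis as a labelled sensitivity analysis. Replace a missing access grade by the mean of the observed access grades in that university, both arms pooled, so that no student is dropped. Reconcile the three universities in the Abstract with the four elsewhere, so that the university term is defined.

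The cost is SAP wording. University follows from the participant code ranges and the access grade is already collected; its scale and completeness should be checked first. The model uses 4 residual degrees of freedom with four universities (78 to 74) or 3 with three (78 to 75). It does not repair differential loss from the missed-session elimination rule, which is a separate problem.

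### A normality pre-test chooses the between-arm test for each variable, no estimate is named for the promised 95% confidence interval, and neither between-arm test uses the PRE value or university

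*Combined protocol and SAP*

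**What the plan says.** All of this is in the combined protocol and SAP, under STATISTICAL ANALYSIS PLAN OF THE RESULTS.

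- **Gate.** "The Kolmogorov-Smirnov test will be performed to check the normality of the distribution", provided that more than 30 people are in the sample. The plan does not give the significance level of this pre-test or its version. It does not say whether the test is run on the whole sample, by arm, by visit or on residuals, or what is done with 30 people or fewer.
- **Normal branch.** "If the distribution is normal, parametric tests will be performed to assess differences between groups". The between-arm test is the independent-samples t test. Repeated measures ANOVA is assigned to comparisons over time within one group.
- **Other branch.** "If the population does not follow a normal distribution of the variable under study, non-parametric tests will be performed", namely "Friedman's test for paired samples and Kruskal Wallis's test for independent samples".
- **Interval.** "In all cases, a 95% confidence interval" is promised, together with a 0.05 significance level. The quantity that the interval describes is not named in either branch.
- **Descriptive summary.** Mean and SD are given for quantitative variables whichever branch is taken.

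Elsewhere, the sample is 80 and the study calls itself a pilot (CALCULATION OF THE SAMPLE). Allocation is balanced within each university (RANDOM ASSIGNMENT). The variables are measured at PRE, at POST and one month later (DEFINITION OF THE STUDY VARIABLES).

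**The concern.** The analysis of each variable is settled by a test on the trial's own data, so the implied contrast (a difference in means or a comparison of ranks) is not fixed in advance. Two scales in the same report could be analysed differently for reasons unrelated to treatment, such as coarse scoring or the software option used for the pre-test. Where the rank branch is taken, the tests as named leave a p value and no effect size.

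This matters more here than in a confirmatory trial. The stated reason for running a pilot is that no similar studies exist, so an estimate with its interval is a main product.

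A second, separate loss lies in the between-arm tests themselves. Both ignore the PRE measurement, which enters only through within-group comparisons over time. Both also ignore university, although allocation is balanced by it.

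**Working it through.** **Inputs from the documents:** N = 80, taken as 40 per arm; significance level 0.05, taken as two-sided; three measurement times. The plan gives no SD, effect size, correlation or power, and N has no calculation to reproduce.

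**Assumptions:** outcome shapes and SDs as stated below, effect 0.5 SD, PRE-POST correlation 0.6, no dropout.

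**1. How often the gate sends a variable to the rank branch.** Simulated normal scores rounded to whole numbers, pre-test at 0.05. Repeat runs differ by up to about 3 percentage points.

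| Assumed SD | Lilliefors-corrected, n = 40 | Lilliefors-corrected, n = 80 | Uncorrected, n = 40 |
|---|---|---|---|
| 2.5 | 44% | 77% | about 1% |
| 3 | 31% | 57% | below 1% |
| 10–12 | about 6–9% | about 6–9% | about 1% or less |

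At n = 80 the uncorrected test rejects the narrow scores more often than at n = 40, but still far less often than the corrected test.

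An SD of 2.5–3 could suit a narrow score, possibly the Pittsburgh total. If summed, the academic stress questionnaire runs from 21 × 1 = 21 to 21 × 5 = 105 and the coping scale from 23 to 23 × 5 = 115. The wider SDs are the more plausible for those two. Cortisol and semester grade are not questionnaire totals; for them skew would matter more than rounding. With lognormal data (log-SD 0.5) the corrected test rejects in 85% of samples of 80.

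**2. Sensitivity to what is tested.** Running the pre-test by arm (either arm rejecting) instead of on the whole sample changed the branch in 6% to 28% of runs, depending on the outcome shape.

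**3. Error rate and decisions.** Pre-test followed by the chosen test gave a type I error of 4.6% to 5.3% across five shapes. With a 0.5 SD shift, the t test and Kruskal-Wallis reached different significance decisions in 6% (normal) to 11% (skewed integer score) of runs.

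**4. Can the rank branch carry an interval?** With two groups, Kruskal-Wallis is the Wilcoxon-Mann-Whitney test without continuity correction (p = 0.01414 from both in a check). It can be inverted using the 40 × 40 = 1,600 pairwise differences:

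c = 1,600/2 − 1.96 × √(1,600 × 81/12) = 800 − 1.96 × 103.9 = 596.3, rounded down to 596.

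Cutting 596 differences from each end gives the Hodges-Lehmann 95% interval. Simulated coverage was 94.9%, and it agreed with the Kruskal-Wallis decision in all 2,000 runs.

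**5. Precision from PRE** (normal approximation, SD units).

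- Unadjusted: SE = √(2/40) = 0.2236; power = Φ(0.5/0.2236 − 1.96) = Φ(0.276) = 61%; interval half-width = 1.96 × 0.2236 = 0.44 SD.
- Adjusted for PRE: SE = 0.2236 × √(1 − 0.6²) = 0.2236 × 0.8 = 0.1789; power = Φ(0.5/0.1789 − 1.96) = Φ(0.835) = 80%; half-width = 1.96 × 0.1789 = 0.35 SD.

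Simulation agrees: about 59% Kruskal-Wallis, 61% t test, 79–80% adjusted model. The gate therefore accounts for about 2 points, and leaving out PRE for nearly 20.

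**The case against.** The strongest reply is that testing normality and then choosing the test is common practice, does no harm to the error rate, and costs almost no power. The calculations bear out the last two points. Mean and SD are also reported for every quantitative variable, so if they are given by arm a reader could form an unadjusted interval. The interval sentence may do no more than set the confidence level. All of this stands, and it limits the point to consistency, interpretability and precision.

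Several stronger readings are tempting but not supported:

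- **That the rank branch can never yield a 95% interval, or that the plan contradicts itself.** Step 4 shows that an interval exists. What is missing is a named estimator.
- **That the data choose the effect measure.** The plan names none in either branch. The data choose the test, and the effect measure follows only by implication.
- **That rank methods must ignore PRE.** In the same scenario, Kruskal-Wallis on change scores had 67–68% power and rank ANCOVA 75–77%. The omission is in both named between-arm tests, not inherent in ranks.
- **That rounding will trigger the gate for most outcomes.** The high rejection rates apply to narrow scores under the corrected test, not to the wide scales.
- **That a switch somewhere is almost certain across arms and visits.** This needs separate corrected tests for each arm and visit, treated as independent, with one rejection enough to switch. The plan states none of these, and its wording is per variable.

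**Conclusion.** The point holds as a recommended improvement. It does not invalidate the trial. The pre-test lets the data pick the between-arm test, leaves the promised interval without an estimate, and can change branch on unstated technical choices: for a narrow score at n = 40, between about 1% or less and 31–44% depending only on the version of the test. There is no material effect on type I error.

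The larger measurable loss is separate from the gate. Without PRE in the comparison, power at the assumed effect is about 59–61% instead of 79–80%, and the interval is a quarter wider (0.44/0.35 = 1.25). That figure rests on the assumed correlation of 0.6 and shrinks as the correlation falls. The rejection rates rest on assumed SDs and shapes. None of these values is given in the documents.

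**What to change.** 1. Delete the normality gate.
2. State in advance one between-arm analysis for each quantitative outcome: the mean difference adjusted for university and for the PRE value where one is measured, with 95% CI. Semester grade has no PRE value; the university-access grade already collected in the sociodemographic questionnaire could serve as its covariate.
3. Say that the 95% interval refers to this difference.
4. Keep a rank-based comparison with a Hodges-Lehmann 95% interval, or a bootstrap interval for the mean difference, as a labelled sensitivity analysis reported whatever the shape of the data.

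The cost is SAP wording only. The PRE values, university and access grade are already collected. The model spends few degrees of freedom: intercept, arm, PRE and three university terms leave 80 − 6 = 74 with complete data.
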